9 SAFETY EVALUATION

The primary safety endpoint is incidence of all serious adverse events. An exploratory comparison will assess dosing symptoms as reported on the specific dosing symptom CRF. Note that as described above no adjustment for multiple comparisons will occur here as these are safety outcomes and detection of any potential signal is of interest.

9.1 Adverse Events

Adverse events are collected on all participants throughout the course of the study. Participants are provided a daily diary card (called a dosing symptom log) to record treatment-related events which are captured on specific dosing symptom CRFs. Adverse events related to OFCs are captured on a specific CRF as are adverse events related to accidental (or purposeful) food ingestion (i.e., food allergy episodes or FAEs).

9.1.1 Solicited Adverse Events and Symptoms – Dosing Symptoms

Symptoms reported on the dosing symptom CRFs are considered treatment related for the purpose of analysis. Systemic symptoms are recorded as mild, moderate or severe.

The key outcome of interest is symptom free doses (defined as no oral pharyngeal or systemic symptoms). Exclusion of oral pharyngeal symptoms will also be considered. Other safety outcomes of interest include doses with moderate and/or severe reactions. Finally, doses requiring treatment will also be described with a focus on doses requiring epinephrine.

Symptoms will be reported per dose, per participant, and proportion of doses per participant. The latter will be calculated by dividing the number of doses with each symptom by the total number of doses the participant received. Formal comparisons of safety outcomes will occur on this measure although significance testing may be performed on other measures if warranted. Proportion of doses with symptoms per participant will be compared using the Wilcoxon Rank Sum test to do pairwise comparisons between treatment groups.

Finally, tables will be broken down by treatment, location, and timing (pre-Week 52 vs. post-Week 52) to illustrate potential dose level and temporal treatment effects.

9.1.2 Other Adverse Events

As described above, non-treatment related adverse events are captured separately and described below.

9.1.2.1 OFC Symptoms

At each OFC the dose limiting symptoms and severity are captured on a specific CRF. Symptoms will be reported for each OFC by initial randomization group. Treatment administered during the OFC (especially any epinephrine use) will be described.

9.1.2.2 Food Allergy Episodes

Food exposure related reactions are captured on the food allergy episode (FAE) CRF. The frequency, severity, and epinephrine use during such reaction will be described, as well as eliciting allergen, and shown by treatment group. Further details on egg related exposures will be provided as necessary.

9.1.2.3 Other Treatment Emergent Adverse Events

Frequency, severity and resolution of other treatment emergent adverse events will be described by treatment group, system organ class and preferred term.

9.2 Deaths, Serious Adverse Events and other Significant Adverse Events

The proportion of participants experiencing a SAE will be estimated within each group. Pairwise comparisons between treatment groups will be performed using Barnard's exact unconditional test at the two-sided 5% level. If multiple SAEs are observed within a participant, alternate methods to account for the multiple events will be considered. If SAEs are infrequent (e.g. 1 or 2 events throughout the study), then hypothesis testing may not be performed. SAEs will also be described by relatedness to study product or procedure.

9.3 Pregnancies

Given the age of the study population, pregnancies are unlikely to be observed. Any participant becoming pregnant will immediately terminate study treatment. Descriptive information about any pregnancies that occur will be provided.

9.4 Clinical Laboratory Evaluations

No safety laboratory results will be systematically collected as part of this trial.

9.5 Vital Signs and Physical Evaluations

No data on vital signs will be systematically collected. Height and weight are collected as part of the study and may be considered as potential factors if of scientific interest.

9.6 Concomitant Medications

Concomitant medications will be collected and described.

10 PHARMACOKINETICS

No pharmacokinetics will be analyzed in this study.

11 MECHANISTIC ANALYSES

11.1 Skin Prick Test

SPTs are performed at baseline, Week 52 and Year 2. SPT results and changes from baseline will be reported at each of these timepoints by treatment group and by Year 2 sustained unresponsiveness status.

Change from baseline at Week 52 and Year 2 will be compared between treatment groups and by Year 2 sustained unresponsiveness status using the Wilcoxon Rank-Sum test to do pairwise group comparisons. Repeated measures model may be fit using the post-baseline timepoints and adjusted for baseline value, treatment and visit to assess any treatment effect or Year 2 sustained unresponsiveness status effect on SPT

measures. An appropriate covariance structure will be selected (with preference given to unstructured models).

11.2 Immunoglobulin Results

Egg specific IgE, IgG4, and total IgE are measured at baseline, Week 12, Week 24, Week 52, Month 16, Month 20, Year 2, Month 26 and Month 30. Percent egg-specific IgE and IgG4/IgE ratio will be calculated as described in Section 3.3 above. Immunoglobulin results and changes from baseline will be reported at each of these timepoints by treatment group and by Year 2 sustained unresponsiveness status.

Change from baseline will be compared between treatment groups and by Year 2 sustained unresponsiveness status using the Wilcoxon Rank-Sum test to do pairwise group comparisons. A repeated measures model will be fit using the post-baseline timepoints except for the Month 30 visit (which is after the final OFC) and adjusted for baseline value, treatment or Year 2 sustained unresponsiveness status, and visit to assess any treatment effect or Year 2 sustained unresponsiveness effect on immunoglobulin measures. An appropriate covariance structure will be selected (with preference given to unstructured models). If there are too few subjects who have completed the Year 2 sustained unresponsiveness OFC to allow for a reasonable model fit, the model may be adjusted accordingly.

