7.5.4 Notifying the Institutional Review Board and Ethics Committee

The investigator will ensure the timely dissemination of all AE information, including expedited reports and DSMB safety reviews, to the IRB and EC in accordance with applicable local regulations and guidelines.

8. Mechanistic Assays

Complementary studies will be performed to measure cellular and humoral immune responses at baseline and longitudinally. These assays have been selected based on hypothesized mechanisms of sustained unresponsiveness induction. The assays to be performed include:

- immune phenotyping of antigen-specific T cells, with a focus on cytokine production and homing molecule expression, in peripheral blood by FACS
- systemic and antigen-induced basophil activation assays
- measurement of whole antigen and epitope-specific IgE and IgG levels
- transcriptional analysis of whole blood and allergen re-stimulated PBMCs

The phenotype of antigen-specific T cells will be monitored at baseline and throughout immunotherapy using freshly isolated peripheral blood mononuclear cells re-stimulated with allergen *in vitro*. Phenotyping will be performed by flow cytometry, and will assess cytokine profile and chemokine receptor expression in antigen-responsive CD154+ CD4+ T cells. Additional phenotyping will be performed by transcriptional analysis of RNA isolated from the allergen-restimulated peripheral blood mononuclear cells.

To perform these assays, blood specimens will be obtained at screening (Visit 00), at 3 months (Visit 02), 6 months (Visit 03), at the 1 year 7444 mg egg white protein OFC (Visit 04), at the 2 year desensitization OFC (Visit 07), prior to the sustained unresponsiveness portion of the 2 year challenge and approximately 6 months after the sustained unresponsiveness challenge.

Subjects that pass the 2 year 7444 mg egg white protein OFC will stop their Egg OIT dosing and return in approximately 8-10 weeks for a 7444 mg egg white protein OFC off therapy (Visit 08) to test for sustained unresponsiveness and have a mechanistic blood test. Blood volumes must be no more than 50 cc in a day.

In summary, all 130 subjects entering the study will have specimens drawn as specified in this section.

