Appendix 1.A. Schedule of Events - Egg OIT Subjects

¹Performed only for subjects who pass the screening baked egg OFC.

² Egg OIT subjects will have initial escalation to at least 3 mg egg white solid on Day 1, return Day 2, return Day 3 if symptoms, return for dose escalation every 2 weeks until dose of 25 mg egg white solid is reached (12 mg for Egg OIT Assignment group).

³ Egg OIT subjects will have escalation visits every 2 weeks, unless epinephrine is administered as described in Section 6.4.1. Phone calls will occur 1 week after each escalation visit to assess dosing compliance and symptoms.

⁴ Only prior to any OFC, at baseline, a peak flow rate may be performed if spirometry results cannot be obtained.

⁵ Egg OIT subjects have 44 weeks maximum to reach highest tolerated dose ≥350 mg egg white solid. Subjects may escalate after 1 year OFC if they have not reached 2500 mg of egg white solid.

⁶For females of childbearing age.

⁷ In Clinical Research Center or monitored clinic setting.

- ⁸ Blood draws will not exceed 50 cc in a day but no more than 5cc/kg in a day or 9.5cc/kg in an 8 week period.

- ¹⁰ All mechanistic blood draws are performed prior to any oral food challenges. ¹⁰ If baked egg challenge is failed, the first 40 subjects will go directly to Egg OIT treatment. ¹¹ Daily home dosing for Egg OIT. Phone calls will occur monthly in between visits once maintenance is reached.

¹² Discontinue Egg OIT.

¹³ Only if desensitization challenge is passed, a repeat challenge off therapy in approximately 8-10 weeks will be performed.
¹⁴ Subjects who pass the sustained unresponsiveness oral food challenge will return for follow-up outlined in appendix 1-D
¹⁵ All subjects will be annually contacted by telephone starting 3 years after randomization, through a maximum of September 2018.

Procedure	Visit 00 Screening	Visit 00A Baseline ¹	Visit 01 ²	Visit 02 3 month (12 weeks)	Visit 03 6 month (24 weeks)	Month 9 Study Assessment ¹⁰	Visit 04 1 year (52 weeks)	Visit 05 16 month (68 weeks)	Visit 06 20 month (84 weeks)	Visit 07 2 year Desensitization ⁸ (104 weeks)	Visit 08 2 year sustained unresponsiveness ^{9,11} (112-114 weeks)	Visit F 03 3 year long term follow- up ¹²	Visit F 04 4 year long term follow up ¹²	Visit F 05 5 year long term follow up ¹²
Medical/Allergy History	х			x	X		х	x	x	х	Х			
Spirometry ³	x													
Physical Exam	х						х			х	Х			
Peak Flow Rate	х	х					Х			Х	х			
Pregnancy Test ⁴	x	х					х			x	х			

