Appendix 1.D. Egg Sustained Unresponsiveness Long Term Follow-up

Study Visit	Visit F 01 ²	Visit F 02 ²
Study Visit	3 months post final OFC Phone Assessment	6 months post final OFC In person
Egg Related Diet History	Х	Х
Egg reaction history	Х	Х
Blood draw with Processing ¹		50cc

¹Blood draws will not exceed 50 cc in a day but no more than 5cc/kg in 24hrs or 9.5 cc/kg in 8 weeks. ²Visit F 01 and F 02 are to be completed by subjects who pass the sustained unresponsiveness oral food challenge.

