6.3 Analysis Populations

The efficacy analysis population will consist of randomized participants who initiate treatment as well as all participants enrolled in the eOIT – Assigned group who initiate treatment. The safety population may vary based on time period and will consist only of treated participants. Mechanistic analyses will consider those with available samples.

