11.3 Activated Basophil Analysis

Activated basophil outcomes will be constructed as described in Section 3.3. Activated basophils will be measured at baseline, Week 12, Week 24, Week 52, Month 16, Month 20, Year 2, Month 26 and Month 30. Activated basophil results for each stimulation level and changes from baseline will be reported at each of these timepoints by treatment group and by Year 2 sustained unresponsiveness status.

Change from baseline will be compared between treatment groups and by Year 2 sustained unresponsiveness status using the Wilcoxon Rank-Sum test to do pairwise group comparisons. A repeated measures model will be fit using post-baseline timepoints except for the Month 30 visit (which is after the final OFC) and adjusted for baseline value, treatment or Year 2 sustained unresponsiveness status and visit to assess any treatment effect or Year 2 sustained unresponsiveness status effect on basophil measures. An appropriate covariance structure will be selected (with preference given to unstructured models). If there are too few subjects who have completed the Year 2 sustained unresponsiveness OFC to allow for a reasonable model fit, the model may be adjusted accordingly.

For each of the egg stimulant levels within each treatment group, a Signed Rank test will be done for the egg value minus IL-3 (negative control), the anti-IgE value (positive control) minus IL-3, and the anti-IgE value minus the egg value at each time point to see if these values are significantly different than zero. A significant difference for egg minus IL-3 or anti-IgE minus IL-3 would indicate a response to egg or to beads, respectively. A significant difference for anti-IgE minus egg would indicate that the response was significantly different for anti-IgE than for egg.

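### SAP 8.3.3 and 11.2–11.4 allow between-arm Wilcoxon tests at off-therapy visits that only responders reach, so these tests are not randomised comparisons

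*SAP*

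**What the plan says.** **Markers.** SAP 11.2 (immunoglobulins) and 11.3 (basophils) list baseline, Weeks 12, 24 and 52, Months 16 and 20, Year 2, Month 26 and Month 30. SAP 11.4 (flow cytometry) omits only Months 16 and 20. SAP 11.2 states: "Immunoglobulin results and changes from baseline will be reported at each of these timepoints by treatment group and by Year 2 sustained unresponsiveness status". It continues: "Change from baseline will be compared between treatment groups and by Year 2 sustained unresponsiveness status using the Wilcoxon Rank-Sum test". No test visit is named. SAP 11.1 (skin prick test), by contrast, names Week 52 and Year 2. Month 30 is set aside only for the model: "A repeated measures model will be fit using the post-baseline timepoints except for the Month 30 visit (which is after the final OFC". SAP 6.3 fixes the population: "Mechanistic analyses will consider those with available samples".

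**Who gives the late samples.** Visit 08, labelled about 26 months in Protocol Appendix 1.C, is conditional in both arms: "Only if desensitization challenge is passed, a repeat challenge off therapy in approximately 8-10 weeks will be performed" (Appendix 1.A; same rule in 1.B). Protocol Section 8 places one more draw "approximately 6 months after the sustained unresponsiveness challenge". In Appendix 1.D that is Visit F 02, and F 01 and F 02 "are to be completed by subjects who pass the sustained unresponsiveness oral food challenge".

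**SCD.** SAP 8.3.3 plans pairwise Wilcoxon tests of SCD change from baseline to every protocol OFC. The rule in SAP 3.3 that non-attenders are failures covers the binary endpoints and assigns no SCD.

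**The concern.** Passing the Year 2 OFC, and later the off-therapy OFC, are outcomes of treatment. If the arms pass at different rates, the arm with fewer passers contributes a more strongly selected group. A marker that tracks tolerance can then differ between arms among passers with no treatment effect on the marker, and a real effect can be masked. The trial expects both ingredients: it plans SU rates of 40% and 70%, and its mechanistic hypotheses link markers to clinical outcome.

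For SCD the problem is more direct. Off-therapy SCD exists only for children already shown to tolerate 7444 mg on therapy, so an attender-only contrast can hide or enlarge the arm difference in SU. A p-value by arm at these visits invites a randomised reading that the data cannot support.

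**Working it through.** **Plan's own figure.** 48 per arm, 40% vs 70%, two-sided 5% (Protocol 9.3, SAP 5). Power = Φ{[0.30·√48 − 1.96·√(2·0.55·0.45)] / √(0.40·0.60 + 0.70·0.30)} = Φ{(2.078 − 1.379)/0.671} = Φ(1.04) = 85%. The stated power reproduces. The documents give no operating figure for the Wilcoxon tests.

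**Which visit is Month 30?** Visit 08 is at weeks 112–114 (Appendix 1.A and 1.B). Six months (26 weeks) later is weeks 138–140; divided by 52/12 weeks per month, that is about Month 32. F 02 is the only protocol draw after the final OFC, so it is the likeliest match, but the labels do not agree.

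**Assumptions.** No document gives a Baked Egg on-therapy pass rate or a marker–tolerance correlation (ρ), so both are ranged. Egg OIT is set at 75%, the prior trial's on-therapy result at 22 months (30/40, Protocol 1.1). Tolerance and marker are bivariate normal, with no treatment effect on the marker.

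**Selection gap.** With pass rates p_B and p_E, the expected marker difference among passers is ρ × [φ(z_B)/p_B − φ(z_E)/p_E] SD, where Φ(z) = p. At 45% vs 75%: 0.880 − 0.424 = 0.456, so 0.456ρ SD. At 40% vs 70% (the planned SU rates, for Month 30 if it is F 02): 0.966 − 0.497 = 0.469ρ SD.

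**Rejection with no true effect**, nominal 1%, 48 per arm, 20,000 simulated trials per setting:

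| Pass rates (Baked Egg / Egg OIT) | Gap ÷ ρ | ρ = 0.3 | ρ = 0.5 | ρ = 0.7 |
|---|---|---|---|---|
| 45% / 75% | 0.456 | 1.8% | 4.0% | 9.3% |
| 50% / 75% | 0.374 | 1.5% | 3.2% | 6.6% |
| 60% / 75% | 0.220 | 1.2% | 1.8% | 2.5% |
| 65% / 75% | 0.146 | 1.0% | 1.1% | 1.7% |
| 75% / 75% | 0 | 1.0% | 0.9% | 0.9% |
| 40% / 70% (Month 30; about 19 vs 34 children) | 0.469 | 1.8% | 3.9% | 9.2% |

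**Lower SU rates.** The prior trial's SU was 11/40 = 27.5%. Keeping the planned ratio, Baked Egg would be 27.5% × 40/70 = 15.7%. Month 30 rejection is then about 0.8%, 0.9% and 1.6%. The gap is still 1.530 − 1.213 = 0.317ρ SD, but only about 8 vs 13 children remain (48 × 0.157 and 48 × 0.275), so the test rarely rejects.

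**Off-therapy SCD.** SU among attenders = SU rate ÷ on-therapy pass rate. For Egg OIT this is 0.70/0.75 = 93%. The true SU difference is 30 points in every row. Simulation: 4,000 trials, two-sided 5%. Assumed: baseline SCD uniform over challenge steps 0–444 mg; off-therapy SCD of those failing uniform over 0–4444 mg.

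| Baked Egg pass rate | SU among Baked Egg attenders | Difference among attenders | Rejection, attenders only |
|---|---|---|---|
| 45% | 0.40/0.45 = 89% | 4 points | about 6% |
| 60% | 0.40/0.60 = 67% | 27 points | about 47% |
| 75% | 0.40/0.75 = 53% | 40 points | about 86% |

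Had all 48 per arm been challenged, rejection would be about 73%. In a separate run with untested children scored as no change, and pass rates of 45–60% (Baked Egg) and 75–90% (Egg OIT), it was 79% to 88%, against 5% to 12% among attenders only.

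**The case against.** **The mechanistic tests are not explicitly ordered at Months 26 and 30.** True. Where the SAP wants per-visit testing it can say so, as with the Signed Rank tests in 11.3 ("the anti-IgE value minus the egg value at each time point"), and the sentence about reporting at each timepoint governs reporting. A reader might infer an explicit instruction; the text does not give one. What stands is the natural reading: both visits are listed, the next sentence sets no limit, 11.1 does set one, and the Month 30 exclusion is confined to the model.

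**Month 30 is not confirmed as responder-only.** Also true. A reader might take that as settled, but no document maps it and the timing is off by about two months. Protocol Section 8 also says that all 130 subjects will have the specimens specified there. That sentence does not undo the attendance conditions in the appendices, but it adds to the need for a definition.

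**SAP 6.5 allows suitable methods if missing-data problems emerge.** The clause is generic. Children who are never scheduled for a visit are a design feature, foreseeable now.

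**The scenarios mix sources.** The 75% pass rate and the 70% SU rate together imply that 93% of passers keep SU; in the prior trial it was 11/30 = 37%, after a shorter break. The objection stands, so the figures are a range and not a forecast.

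**Little depends on it.** Protocol 9.5 calls the mechanistic work exploratory, 8.3.3 is exploratory, and the primary chi-square already tests SU properly. This limits the priority, though marker changes are also listed as secondary endpoints (Protocol 3.2, SAP 3.2).

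**Conclusion.** The point holds in this form. Between-arm Wilcoxon tests at the off-therapy OFC (SCD) and at Month 26, and at Month 30 if it is F 02, compare children selected on a post-randomisation outcome. They describe those children validly but do not test the randomised comparison. That follows from the attendance rules. The size does not: over the range tabulated, marker rejection runs from about nominal to roughly 9% at a nominal 1% level, and attender-only SCD rejection from about 5% to 85% for one and the same SU difference. Marker inflation is material only if pass rates differ widely and the marker tracks passing closely.

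If Month 30 is F 02, the SU-status test there has essentially no failure group; a child who passes the OFC but fails the open feeding is the only likely exception.

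Two wider inferences are not supported. The primary endpoint is not affected, because non-attenders count as failures. Nor are the SCD comparisons at Week 52 and Year 2 free of selection: SAP 4.1 limits both OFCs to children still on treatment, whereas Protocol 6.4 speaks of all subjects, and several discontinuation rules (Protocol 4.3.1 and 6.4) apply only to Egg OIT. The repeated-measures model keeps Month 26 but also uses the earlier visits, so it is less exposed than a stand-alone test.

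This is a wording change worth considering, not a threat to the trial's main conclusion.

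**What to change.** **SAP 11.2–11.4.** Name the Wilcoxon test visits and limit treatment-group tests to visits through Year 2 (Visit 07). Report Months 26 and 30 by arm descriptively, labelled as responder subsets. State which protocol visit Month 30 is. If it is F 02, drop the SU-status test there. Keep the Month 26 SU-status test, labelled as being among children who passed the Year 2 OFC.

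**SAP 8.3.3.** Limit between-arm tests of SCD change to Baked Egg vs eOIT-Randomized at Week 52 and Year 2. Report the off-therapy OFC descriptively among attenders. For Week 52 and Year 2, either state how unchallenged children are scored (for example, as no change) or label the tests as being among those challenged. Reconcile SAP 4.1 with Protocol 6.4 on who is challenged.

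**Secondary point.** Appendix 1.A indicates that eOIT-Assigned children have no initial egg OFC and hence no baseline egg-white SCD, although Protocol 6.3 and 6.4 can be read otherwise. Compare that group on attained follow-up SCD instead of change.

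**Cost.** SAP text only: no new data, visits or procedures. The downside is fewer p-values at the off-therapy visits; the data there are still reported.

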To effectively address the Primary and Secondary Objectives of this interventional study, we will enroll subjects, age 3 through 16 years, either sex, any race, any ethnicity with a serum IgE [UniCAPTM] to egg of \geq 5 kU_A/L [determined by UniCAPTM within the past 12 months]. All subjects will have documented consent and assent as is appropriate. Females of childbearing age will use appropriate birth control. These subjects will be recruited from 5 sites. All eligible subjects will receive the double-blind placebo controlled baked egg OFC. Approximately the first 40 individuals who do not pass this initial baked egg food challenge will be assigned to Egg OIT. Enrollment in this group will be capped at approximately 40 individuals though those consented but not yet challenged when this group reaches 40 will be allowed to proceed and if they fail the baked egg challenge will be assigned to the egg OIT assignment group. This may result in slightly over 40 cases in this group which is acceptable. Individuals who pass the baked egg OFC will then have an initial egg OFC. Those who have dose-limiting symptoms at a cumulative dose of \leq 1444 mg egg white protein will be randomized 1:1 to Baked Egg or Egg OIT. Those who successfully consume more than 1444 mg of egg white protein on the OFC will not be eligible for the study and will be followed per local standard of care.

Those assigned or randomized to Egg OIT will escalate the dose of egg white solid to achieve the desired maintenance dose of 2500 mg. Those randomized to the Baked Egg group will continue on the baked egg product for the remainder of the study.

Throughout this protocol, the doses of egg white solid for Egg OIT are given in milligrams of egg white solid, not egg white protein. It is estimated that 1 mg egg white solid is equivalent to approximately 0.70 mg of egg white protein.

A schematic is presented below:

For the purposes of this study, clinical details and blood samples will be collected at specified intervals. If a subject is removed from therapy because of failing escalation or build-up, a blood sample for mechanistic studies will be obtained within approximately 1 week of removal from therapy.

Subjects will have an annual phone follow-up at 1, 2 and 3 years after completing the active portion of the study through September 30, 2018.

The Baked Egg Group

The Baked Egg group will use approximately 2 gm of baked egg as a daily dose throughout the study as described below.

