Once 25 mg egg white solid is tolerated (12 mg in the Egg OIT assigned group), subjects will begin the Clinical Research Center dosing scheme as outlined until 2500 mg of egg white solid is reached. Subjects will return for a supervised dose escalation in the clinic every 2 weeks. Subjects will be called 1 week after each dose escalation visit to assess for dosing compliance and dose reactions. Any dose escalation attempts may be postponed for 1-2 extra weeks based on clinical judgment. An escalation attempt must be made by 4 weeks. Subjects should withhold their daily home dose on the escalation day but should take all other prescribed medications. Note that the daily home dose should be taken as part of a meal. It is recommended that the dose be taken at a consistent time (within a 4 hour time period), and it is critical to take the dose every day. Doses should be separated by at least 12 hours. Subjects who require dosing reduction during the 2 week period will reset their 2 week escalation schedule to maintain the new dose for a 2 week period prior to attempting to escalate again.

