11.4 Flow Cytometry Analysis (CD154+ Cells)

Flow cytometry outcomes will be constructed as described in Section 3.3. Results will be measured at baseline, Week 12, Week 24, Week 52, Year 2, Month 26 and Month 30 and changes from baseline will be reported at each of these timepoints by treatment group and by Year 2 sustained unresponsiveness status.

Change from baseline will be compared between treatment groups and by Year 2 sustained unresponsiveness status using the Wilcoxon Rank-Sum test to do pairwise group comparisons. A repeated measures model of delta egg minus media (value for media stimulant subtracted from value for egg stimulant) will be fit using the post-baseline timepoints except for the Month 30 visit (which is after the final OFC) and adjusted for baseline value, treatment or Year 2 sustained unresponsiveness status, and visit to assess any treatment effect or Year 2 sustained unresponsiveness status effect on flow cytometry measures. An appropriate covariance structure will be selected (with preference given to unstructured models). If there are too few subjects who have completed the Year 2 sustained unresponsiveness OFC to allow for a reasonable model fit, the model may be adjusted accordingly. Within each treatment group, a Signed Rank test will be done for delta egg minus media, delta beads minus media (value for media stimulant subtracted from value for beads stimulant), and delta beads minus egg (value for egg stimulant subtracted from value for beads stimulant) at each time point to see if these delta values are significantly greater than zero. A significant difference for delta egg minus media or delta beads minus media would indicate a response to egg or to beads, respectively. A significant difference for beads minus egg would indicate that the response was significantly different for beads than for egg. (Note that media is the negative control and beads is the positive control for the assay.)

Additionally, correlations with egg specific immunoglobulin results will be explored. Spearman rank correlations may be estimated. Immunoglobulin measures may also be considered as covariates in the repeated measures models to assess the contemporaneous associations.

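### The repeated-measures marker models in SAP 11.2 to 11.4 list no group-by-visit term, so one coefficient averages dose ramp, maintenance and off-therapy visits

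*SAP*

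**What the plan says.** SAP 11.2 (immunoglobulins) will fit a repeated-measures model to the post-baseline visits other than Month 30, "adjusted for baseline value, treatment or Year 2 sustained unresponsiveness status, and visit to assess any treatment effect" or an effect of sustained unresponsiveness (SU) status. SAP 11.3 (basophils) and 11.4 (flow cytometry) list the same terms. No treatment-by-visit or status-by-visit term is listed in any of them.

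Immunoglobulins are "measured at baseline, Week 12, Week 24, Week 52, Month 16, Month 20, Year 2, Month 26 and Month 30", and basophils follow the same schedule, so seven post-baseline visits enter the model once Month 30 is left out. Flow cytometry is done at "baseline, Week 12, Week 24, Week 52, Year 2, Month 26 and Month 30", so five enter.

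On dosing, Protocol Section 3 says "The Baked Egg group will use approximately 2 gm of baked egg as a daily dose throughout the study". For Egg OIT, Protocol 6.4 says "Subjects will return for a supervised dose escalation in the clinic every 2 weeks" until 2500 mg of egg white solid is reached.

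Two stated aims bear on this. Protocol 9.5 lists temporal changes in immune parameters and their association with each treatment. Protocol 9.4 and SAP 5 ask whether response profiles are parallel in the two Egg OIT strata.

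**The concern.** A model with baseline, group and visit as main effects assumes the same group difference at every visit. The design gives reason to doubt that. In the randomized Egg OIT arm the first two modelled visits fall in the dose ramp and the later ones at or near maintenance, while the comparator dose is planned as constant. Month 26 comes after 8-10 weeks without treatment and exists only for a subset selected by outcome.

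The single coefficient then describes no particular visit and can understate a difference that has developed by Week 52 or Year 2. It also takes parallel profiles as given, so it cannot test whether they are parallel. The status model has the same structure.

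The practical stake is how markers are classified. Protocol 2.1 treats assays with a detected treatment difference as treatment-affected and then examines whether immune states predict clinical outcome. An averaged coefficient judged at the 0.01 level could place a marker on the wrong side of that line.

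**Working it through.** **Step 1: the plan's own schedule.** The Protocol synopsis gives about 32 weeks of escalation from 25 mg. In the Section 3 dose table, 25 mg is dose 9 and 2500 mg is dose 25. That is 25 − 9 = 16 steps, and 16 × 2 weeks = 32 weeks. The figure reproduces.

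**Step 2: dose held before each early visit.** Protocol Appendix 1.C has blood drawn before that day's dose, so the preceding home dose is the relevant one.
- Week 12: five steps taken (Weeks 2 to 10), dose 14 = 225 mg; 225/2500 = 9.0%.
- Week 24: eleven steps taken (Weeks 2 to 22), dose 20 = 830 mg; 830/2500 = 33.2%.
- From Week 32: 2500 mg.

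The assigned group starts at 12 mg and is one step behind: 150 mg (6.0%) and 700 mg (28%), reaching 2500 mg at Week 34.

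**Step 3: what the single coefficient estimates.** With visit-specific differences d and within-child covariance V, the estimate is the weighted mean w′d, with w = V⁻¹1 / (1′V⁻¹1).

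Assumptions, none of them in the documents: marker effect proportional to current dose; Baked Egg effect zero; complete data; full effect at every visit from Week 52, including Month 26. Then d as a share of the late difference is 0.09, 0.332, 1, 1, 1, 1, 1 for seven visits, and 0.09, 0.332, 1, 1, 1 for five. Under equal correlation the weights are equal:
- seven visits: (0.09 + 0.332 + 5)/7 = 5.422/7 = 0.77
- five visits: (0.09 + 0.332 + 3)/5 = 3.422/5 = 0.68

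Share of the late difference recovered, by correlation structure:

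| Correlation | 7 visits | 5 visits |
|---|---|---|
| Equal, 0.5 or 0.7 | 0.77 | 0.68 |
| Decaying, 0.5 per 26 weeks | 0.70 | 0.69 |
| Decaying, 0.8 per 26 weeks | 0.63 | 0.63 |

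Leaving out Month 26 gives 0.62-0.74 (immunoglobulins, basophils) and 0.61-0.67 (flow cytometry). The SAP prefers an unstructured covariance, so the actual weights will depend on the data.

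**Step 4: if Baked Egg is also active.** Let r be the Baked Egg effect divided by the full-dose Egg OIT effect, and a the recovered share from Step 3. The estimate as a share of the late difference is (a − r)/(1 − r). For seven visits:
- r = 0.25: 0.50 to 0.70
- r = 0.5: from (0.626 − 0.5)/0.5 = 0.25 to (0.775 − 0.5)/0.5 = 0.55
- r = 0.75: −0.50 to 0.10

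The estimate is zero when r = a, so near-cancellation needs Baked Egg to have about 63-77% of the full-dose Egg OIT effect.

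**Step 5: power.** Take 48 per arm (96 randomized 1:1), 0.01 taken as two-sided, a late difference of 0.7 SD and r = 0. The single coefficient over seven visits has 50-86% power across the structures above; a Year 2 contrast alone has 80%. Averaging shrinks the effect but also reduces variance, so power can move either way.

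**The case against.** **Late differences remain visible.** SAP 11.2 to 11.4 report changes from baseline by group at each timepoint and compare them by Wilcoxon rank-sum test, so an early-late reversal would show. This largely stands. The remaining gap is that these sections do not say at which visits the rank-sum test is run, whereas 11.1 names Week 52 and Year 2. A rank-sum test also gives no baseline-adjusted longitudinal estimate.

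**Dose is not marker response.** Protocol 1.1 says heating destroys conformational epitopes, so comparing milligrams of baked and unheated protein fixes neither the size nor the direction of a marker difference. This stands. A reader might infer that the estimate is necessarily diluted or cancels; the documents do not support that, because they give no marker trajectory or dose-response.

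**The ideal schedule is not every child's schedule.** A reader might infer full dose by Week 52. Protocol 6.4 accepts maintenance from 350 mg upward and allows build-up to resume in year 2, and Protocol Section 3 lets investigators adjust the Baked Egg dose. The 9% and 33% figures describe on-schedule children only.

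**Skin prick testing is different.** A reader might extend the point to SAP 11.1. There, "SPTs are performed at baseline, Week 52 and Year 2", so no visit falls in the first-year ramp, and the model is optional: "Repeated measures model may be fit using the post-baseline timepoints and adjusted for baseline value, treatment and visit". The point does not apply to 11.1.

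**Low stakes.** Protocol 9.5 calls the mechanistic assessments exploratory, and the sample size was not chosen for them. This stands, although the markers do appear among the secondary endpoints in Protocol 3.2 and SAP 3.2.

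**Conclusion.** The point holds for SAP 11.2 to 11.4 as an inexpensive improvement to exploratory analyses. As listed, the models give one average over two ramp visits, the later on-therapy visits and a selected off-therapy visit, and they assume the parallelism that Protocol 9.4 and SAP 5 want examined.

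Under a dose-proportional effect with inactive Baked Egg, that average is roughly 63-77% of the late difference for immunoglobulins and basophils, and 63-69% for flow cytometry. Stronger Baked Egg activity lowers the share, and near-zero estimates need the specific ratio in Step 4. All of this depends on the assumed dose-response, correlation and complete data. No general loss of power follows. The status-by-visit point rests on model structure alone, with no calculation behind it. The primary comparison is unaffected.

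**What to change.** In SAP 11.2 to 11.4:
- Add a treatment-by-visit term to the treatment models and an SU-status-by-visit term to the status models.
- Name the Week 52 and Year 2 contrasts as the model-based effects to report. Under the assumptions in Step 3 these recover the full late difference.
- Report Month 26 separately, as an off-therapy result in children who passed the Year 2 challenge.
- State that the Wilcoxon comparisons are run at each visit.

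This changes wording only. The cost is (visits − 1) × (groups − 1) extra parameters. With Month 26 out of the model and two randomized arms, that is 5 × 1 = 5 for immunoglobulins and basophils and 3 × 1 = 3 for flow cytometry. Intervals would be slightly wider if the group difference really were constant.
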